8.4. Dose Adjustment, Interruption, and Withdrawal from Investigational Product or Study

Investigational product may be temporarily decreased (eg, from 10 mg to 5 mg daily, or by decreasing dosing frequency) or temporarily or permanently stopped based on tolerability concerns. The dose of investigational product should be adjusted back to the maintenance dose in a blinded manner once the issues relating to the lack of tolerability are resolved.

Subjects that discontinue investigational product are expected to continue in the study (and follow the regular visit schedule) until the end of the study, and the study will only terminate at the time when the needed number of adjudicated events has accrued. If a subject reaches an outcome event, he or she should continue the regular visit schedule and continue taking investigational product as long as the subject has not met any of the criteria for mandatory interruption of investigational product outlined in Section 8.4.1, and the Investigator assesses it as safe. In general, subjects should be strongly encouraged to both stay on investigational product and remain in the study until study termination.

8.4.1. Reasons for Additional Monitoring or Mandatory Interruption of Investigational Product

8.4.1.1. Reasons for Additional Monitoring Related to Liver Chemistries

Subjects who develop ALT or AST >2x baseline (and >ULN) or total bilirubin >1.5x baseline (and >ULN) should have repeat testing within 48 to 72 hours to confirm values. Subjects with

persistent elevations (eg, additional lab testing per Investigator discretion) should be closely monitored. Concomitant elevations in total bilirubin or international normalized ratio (INR) with persistent increases in ALT or AST should also be closely monitored.

8.4.1.2. Reasons for Investigational Product Interruption Related to Elevated Liver Chemistries

Development of any of the following clinical laboratory values, without explanation, during the study mandates investigational product interruption:

- AST and/or ALT >3x baseline (and >ULN)
- Total bilirubin >2x baseline (and >ULN)

Repeat testing within 48 to 72 hours to confirm the abnormalities and to determine if they are increasing or decreasing should be performed. Detailed AE information should also be collected and the subject should be investigated for possible causes of the liver chemistry changes, as appropriate. The Investigator should obtain a history of concomitant medications (including nonprescription medications and herbal and dietary supplement preparations) and other possible causes of liver enzyme and bilirubin increases. Any potentially hepatotoxic medications should be identified and discontinued if advisable.

If symptoms persist or repeat testing shows AST or ALT >3x baseline (and >ULN) or total bilirubin >2x baseline (and >ULN), subjects should be followed as clinically indicated depending on other laboratory and clinical signs and symptoms.

For the purposes of this protocol, if the above referenced significant elevation in liver enzyme or bilirubin levels resolve following interruption of investigational product and no other cause for the elevation is identified, the elevations should be assumed to be related to investigational product and investigational product should be discontinued. If the liver enzyme or bilirubin levels do not resolve following interruption of study medication and no other cause for the elevation is identified, it may be assumed that the elevations were due to disease progression and the subject may be re-challenged following a discussion between the Investigator or designee and the Sponsor.

Elevation of liver enzymes or bilirubin is based on comparison to baseline values defined as the mean of all available Screening and Day 0 values, which are the mean of all available evaluations prior to the first administration of investigational product. At least 2 of these samples will be obtained a minimum of 2 weeks apart during the Screening period. Elevations that occur gradually over the course of the study may be indicative of disease progression and should be assessed as clinically appropriate. Liver enzyme and bilirubin elevations that occur over a shorter time, such as within a 6-month period, should be evaluated for drug-induced liver injury as provided in the guidelines below.

If at any time a subject develops signs or symptoms of hepatotoxicity such as new onset fatigue, nausea, vomiting, right upper quadrant pain or tenderness, fever, rash, and/or eosinophilia (>7%) in combination with elevations in liver enzymes, investigational product should be interrupted and liver enzymes monitored until signs or symptoms resolve.

Subjects who develop evidence of severe drug-induced liver injury, which is suspected to be causally related to the investigational product should be discontinued from investigational

product and should not be rechallenged. Severe drug-induced liver injury includes, but is not limited to, functional hepatic impairment, as indicated by rising bilirubin or INR that cannot be explained by progression of disease. Natural progression of the underlying condition and other causal factors, such as a common bile duct stone or development of other concurrent liver disease, should be considered before the investigational product is permanently discontinued.

If after all investigations and actions outlined above have been completed, the Investigator determines that the elevations in liver biochemistries are considered not related to investigational product, the Sponsor must be contacted before investigational product can be reinitiated. Follow-up procedures for subjects resuming treatment, including laboratory evaluations and physical examinations, must be performed after a maximum of 2 weeks of retreatment. Results must be reported to the site as soon as possible so the Investigator can determine if it is appropriate for the subject to continue treatment. In the event the investigational product is required to be discontinued, subjects should be encouraged to continue study visits for continued data collection but may withdraw consent at any time.

The Medical Monitor must be contacted in all cases of persistent liver biochemistry elevations.

All hepatic injury events, regardless of relationship to investigational product, will be adjudicated by the Hepatic Safety Committee (see [Section 13.4](#)).

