5.6. Summary of Known Potential Risks with OCA

The primary AE shown to be related to OCA is pruritus. Pruritus has also been observed in clinical studies with OCA in other indications, as well as in healthy subjects, but with a much lower frequency than that observed in subjects with PBC.

Consistent with the dose-limiting hepatic toxicities observed in the non-clinical studies and the chemical characteristics of OCA as a bile acid and detergent, dose-related but reversible and asymptomatic increases in ALT and AST were observed in healthy volunteers treated with multiple doses of OCA starting at the 100 mg dose (Study 747-102).

In subjects with chronic liver disease such as PBC, hepatobiliary findings including increased transaminases and bilirubin and signs or symptoms of hepatic decompensation such as development of jaundice were observed. These findings were seen more frequently with doses of OCA 10 mg once daily to OCA 50 mg once daily (up to 5x the highest recommended dose). In addition, cholecystitis, including acute cholecystitis, was reported in association with treatment with OCA.

Lipoprotein changes have also been observed with OCA dosing, including a decrease in high density lipoprotein (HDL) and an increase in low density lipoprotein (LDL). Notably, in subjects with PBC, the decrease in mean HDLc levels occurred early and stabilized within 3 months after which time levels generally remained constant over the course of treatment. The average levels of HDLc remained within normal limits. Commensurate with decreases in HDLc,

decreases in total cholesterol were observed in subjects with PBC, while LDLc concentrations remained comparable to baseline and placebo in OCA-treated subjects with the exception of a modest transient and early rise after initiation of treatment.

Refer to the Investigator's Brochure (IB) for additional information regarding the known potential risks with the investigational product.

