12.1.10. Follow-Up of AEs and SAEs

All AEs must be followed during the course of the study until the AE resolves, is no longer of clinical concern, has stabilized or is otherwise explained, or the subject is lost to follow up.

AEs ongoing at the final visit that are deemed to be “possibly, probably, or definitely” related or of other clinical significance must be followed for as long as necessary to adequately evaluate the safety of the subject or until the event stabilizes, resolves, or is no longer of clinical concern. If resolved, a resolution date for the AE should be documented on the CRF. The Investigator must ensure that follow up includes any supplemental investigations indicated to elucidate the nature and/or causality of the AE. This may include additional laboratory tests or investigations, or consultation with other healthcare professionals, as considered clinically appropriate by the Investigator.

All subjects showing possible drug-induced liver injury should be followed until all abnormalities return to normal or to the baseline state. Drug-induced liver injury may develop or progress even after the causative drug has been stopped. Results should be recorded in the CRF.

Note that longer follow-up can sometimes reveal an off-drug repetition of what had appeared to be drug-induced liver injury, indicating that liver injury was related to underlying liver disease.

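### Sections 8.4.1.2 and 13.4 contradict each other on which liver injuries the Hepatic Safety Committee adjudicates, and Section 8.4.1.2 also offers persistence off product as a ground for presuming progression

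*Protocol*

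**What the plan says.** **Committee remit.** Section 8.4.1.2 closes by assigning all hepatic injury events to the Hepatic Safety Committee, irrespective of relationship to product, and refers the reader to Section 13.4. Section 13.4 is narrower in two places. Its lead-in restricts the hepatic injury category to drug-related events, and its bullet gives the committee suspected drug-related events only.

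**Persistent elevations.** Section 8.4.1.2 mandates interruption for an unexplained AST or ALT above 3x baseline, or bilirubin above 2x baseline (each also above ULN). If values resolve off product and no other cause is found, the elevation is to be assumed related and product is discontinued. If they do not resolve and no other cause is found, "it may be assumed that the elevations were due to disease progression and the subject may be re-challenged following a discussion" between Investigator and Sponsor.

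The same section adds safeguards:
- Faster rises go to work-up: "Liver enzyme and bilirubin elevations that occur over a shorter time, such as within a 6-month period, should be evaluated for drug-induced liver injury".
- Severe injury suspected to be product-related may not be re-challenged.
- Restart after a not-related determination is governed by a paragraph that opens "If after all investigations and actions outlined above have been completed". It requires Sponsor contact and a check after at most 2 weeks of retreatment.
- "The Medical Monitor must be contacted in all cases of persistent liver biochemistry elevations".

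Section 12.1.10 states that "Drug-induced liver injury may develop or progress even after the causative drug has been stopped" and that "All subjects showing possible drug-induced liver injury should be followed until all abnormalities return to normal or to the baseline state". Section 5.6 records that, in PBC and other chronic liver conditions, "hepatobiliary findings including increased transaminases and bilirubin and signs or symptoms of hepatic decompensation such as development of jaundice were observed", and that "These findings were seen more frequently with doses of OCA 10 mg once daily to OCA 50 mg once daily".

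**The concern.** The remit matters because the committee is blinded and independent of the sites. If it sees only cases already suspected to be drug-related, the relatedness judgement decides which cases are reviewed. An injury labelled as progression is the kind of case an independent committee should look at, and under Section 13.4 it may not arrive.

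The presumption in Section 8.4.1.2 matters because it steers that label. The subject whose tests stay abnormal off product is the one for whom the protocol offers progression as an explanation and allows restart. Section 12.1.10 says drug injury can behave the same way, so persistence does not separate the two explanations. What is at stake is re-exposure of a subject with unresolved drug injury.

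**Working it through.** No figure in the protocol bears on this point, so the check is a reading of the current sections against one another.

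**1. Remit.** Take a hepatic injury that the Investigator judges to be progression.
- Under Section 8.4.1.2, relationship is irrelevant, so it is adjudicated.
- Under Section 13.4, only suspected drug-related injury qualifies, so it may not be.

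Since Section 8.4.1.2 cites Section 13.4, a reader who follows the reference finds the narrower rule. The summaries of changes suggest how this arose. The Section 13.4 wording dates from Version 3 (Appendix F), while the Section 8.4.1.2 wording was broadened in Version 4 (Appendix H). That history explains the mismatch; the finding rests on the current text alone.

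**2. The presumption against Section 12.1.10.** Section 8.4.1.2 offers non-resolution, with no other cause found, as a ground for assuming progression. Section 12.1.10 says drug injury may develop or progress after stopping. It also notes that longer follow-up can sometimes show underlying disease to be responsible. Taken together, persistence leaves both readings open.

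**3. The presumption against the re-challenge bar.** The bar covers severe drug-induced injury suspected to be product-related. Its stated example is functional impairment shown by a bilirubin or INR rise that progression does not explain. Assuming progression supplies that explanation, so it can take a case out of the example. The list is expressly not exhaustive, so other severe injury stays barred.

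**4. The presumption against the tempo rule.** Gradual rises may suggest progression, and rises within about 6 months go to drug-injury evaluation. The presumption is not limited to gradual rises.

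**5. The restart conditions.** Work-up, a not-related determination, Sponsor contact, Medical Monitor contact and the check by 2 weeks are all required. None of them says that non-resolution is an insufficient basis for the determination itself.

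**6. Size.** Only subjects randomized to OCA can be re-exposed to OCA by restarting investigational product. With 1:1 allocation of 428 subjects (Sections 7.1 and 7.2), 428 / 2 = 214. This is the whole planned arm and serves only as an outer bound. The affected group is an unknown subset: unexplained elevation over threshold, not resolving off product, no other cause found. The documents give no frequency and none is assumed.

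**The case against.** The strongest reply is that Section 8.4.1.2 already handles persistent elevations with care. The presumption is permissive and needs a negative search for other causes and a Sponsor discussion. Restart further needs completed investigations and a positive not-related determination. Section 8.4.1.1 also calls for close monitoring of persistent elevations. All of this stands. A reader might infer that failure to resolve leads directly to re-challenge, or that the protocol has only one sentence on persistent elevations. The text supports neither.

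It can also be said that using response to withdrawal as evidence fits the protocol's causality scheme, since Table 8 in Section 12.1.2 counts improvement on stopping towards Definite and Probable. That is fair. But the Possible category does not require such improvement, so lack of improvement does not make an event unrelated.

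On dose, the Section 5.6 statement spans 10 mg to 50 mg daily, up to 5x the highest recommended dose. The standard maximum here, 10 mg daily (Section 7.3), is the bottom of that range. The statement shows that liver findings are a known risk; it does not show how often they occur at trial doses.

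On the committee, the broader rule is explicit, Section 13.4 looks like unconformed text, and the charter, which is not at hand, may settle it. That limits the consequence but does not remove the contradiction.

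**Conclusion.** Two points hold. First, Sections 8.4.1.2 and 13.4 contradict each other on the Hepatic Safety Committee's remit. The consequence depends on which is followed: if Section 13.4 or a charter drafted to match it prevails, cases judged to be progression can escape blinded adjudication. Second, as a smaller safety correction, Section 8.4.1.2 offers persistence off product as a ground for presuming progression when Section 12.1.10 shows that persistence does not discriminate.

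The number affected is not given and cannot be derived.

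A reader might go further and infer that the committee mismatch changes who is restarted, or that the efficacy analysis is compromised. The documents do not support either. The restart decision lies with the Investigator after Sponsor contact, not with the committee. Subjects off product are expected to remain in follow-up (Section 8.4), and the DMC reviews laboratory data and serious adverse event narratives about quarterly (Section 13.3).

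**What to change.** **Section 13.4.** Change both the lead-in and the Hepatic Safety Committee bullet so that they cover hepatic injury events of any judged relationship to product, as Section 8.4.1.2 already does. Check that the charter agrees.

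**Section 8.4.1.2.** Replace the sentence on non-resolving elevations with: 'Where values stay raised off product and work-up finds no other cause, persistence alone neither establishes disease progression nor excludes drug-induced liver injury. Re-challenge may be considered only under the conditions set out below, and only when the recorded not-related determination rests on evidence beyond non-resolution, for example gradual onset or other signs of progression.' This keeps re-challenge available.

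**Cost.** A wording amendment, a charter check and a site communication. The committee will see a few more cases. A few subjects may restart later or not at all; they stay in the ITT comparison, but less time on product could slightly dilute the treatment effect.

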8.4.1.3. Pregnancy

If a female subject becomes pregnant, she must interrupt treatment with investigational product immediately, but should continue with the study visit schedule. As described in [Section 12.1.11](#) pregnancy is not considered an AE for reporting purposes. The subject may re-start investigational product when she is no longer pregnant or breastfeeding (if applicable) at the discretion of the Investigator and after discussion with the Medical Monitor as described in [Section 12.1.11](#).

8.4.2. Reasons for Mandatory Discontinuation of Investigational Product

8.4.2.1. Liver Transplantation

Subjects who undergo a liver transplant during the course of the study must discontinue investigational product and discontinue the study visit schedule. However, these subjects should be encouraged to consent to the semiannual telephone contact and/or continued record review only to allow for secondary outcome events data to be collected.

8.4.3. Other Reasons for Discontinuation of Study or Investigational Product

The following events are considered appropriate reasons for a subject to discontinue investigational product; however, these subjects are expected to continue in the study until study termination (or at the discretion of the Sponsor):

- Subject begins treatment with commercially available OCA
- The Investigator or Sponsor considers that it is advisable or in the best interest of the subject.

- The occurrence of clinical or laboratory AEs considered by the Investigator to be clinically important safety concerns and related to study drug.
- Withdrawal of consent
 - Consent may be fully withdrawn (in which case the subject discontinues both investigational product and study visits and procedures).
 - Consent may be modified to discontinue study visits but allow semi-annual telephone contact.
 - Consent may be modified to discontinue study visits or semi-annual telephone contact but allow continued access to medical records to assess for suspected major adverse cardiovascular events (MACE) and liver-related clinical outcomes.
 - Early termination procedures should be conducted if the subject withdraws consent (See [Section 9.7.18](#)).

The Investigator is encouraged to contact the Sponsor prior to discontinuing a subject from treatment. The Investigator must notify the Sponsor study monitor by telephone or email as soon as possible if any subject prematurely withdraws from the study.

8.4.4. Withdrawal of Consent

If the subject decides that it is in his/her best interest to discontinue from the study, he or she may withdraw consent. It is fully understood that all subjects volunteer for the study and that they may withdraw their consent to continue in the study at any time.

A reasonable effort must be made to determine the reason(s) for subject discontinuation. This information and date must be recorded in the appropriate case report form (CRF).

8.4.5. Lost to Follow-Up

If a subject fails to return to the clinic for a study visit, and the Investigator ceases to have contact with the subject, he or she will be withdrawn from the study.

A reasonable effort must be made to contact the subject and determine the reason(s) why a subject fails to return for a study visit or is lost to follow-up. This information and date of contact must be recorded in the appropriate CRF.

8.4.6. Subject Discontinuation Notification

The Investigator must notify the Sponsor study monitor by telephone or email as soon as possible if any subject prematurely withdraws from the study. The date when the subject is withdrawn and the reason for discontinuation must be recorded in the CRF. If a subject is “lost to follow up” (fails to return for a visit), a reasonable effort should be made to contact the subject in order to determine why the subject failed to return. This information must be documented in the CRF. If a subject is withdrawn from the study early (regardless of the cause), all of the EOT/EOS evaluations should be performed at the time of withdrawal, as appropriate (See [Section 9.7.18](#), Early Discontinuation and/or Early Termination Procedures).

9. TREATMENT OF SUBJECTS

9.1. Investigational Product Treatment Regimen

The term investigational product refers to either OCA (provided as part of this clinical study) or matching placebo.

Two treatment groups will be evaluated: OCA and placebo. Investigational product will be administered orally. Each dose will be made up of 1 tablet (ie, one 5 mg OCA tablet or one 10 mg OCA tablet, or matching placebo).

Investigational product will be taken orally, up to once daily, for the duration of the study.

All subjects will be instructed to begin dosing on the day after the Day 0 visit (ie, on Day 1) and to take investigational product at approximately the same time of day. Subjects must be instructed to swallow the tablet whole; they must not chew, divide, or crush the tablet.

At each study visit where the daily dose of investigational product is administered at the site, all assessments, except for the post-dose collection of blood samples for the subset of subjects participating in the Month 9 PK assessment, must be completed before administration of investigational product.

